7.5 Secondary Outcomes

An important secondary outcome is time until a composite of (1) adjudicated dementia determined from inperson or phone-based evaluations, (2) adjudicated MCI²⁶ determined from in-person evaluations (3) a 3point drop in the 30-item MMSE administered in-person, or (4) a 3-point drop in a factor score derived from the 10-item MMSE orientation subscale and 11-item Blessed scale administered over the phone and rescaled to be equivalent to the 30-item MMSE. Intervention conditions will be compared for the time until the composite outcome utilizing a discrete-time, cause-specific proportional-hazards model with a complimentary log-log link. The same baseline covariates specified for the mixed effects model will be integrated into the proportional-hazards model. Time on study will be the time scale. As a sensitivity analysis, we will examine variations of the composite outcome that include (1) adjudicated MCI from phone-based evaluations and (2) unadjudicated MCI diagnoses identified algorithmically. In exploratory analyses, we will analyze time until (1) adjudicated dementia or MCI diagnosis and (2) decline in MMSE and Blessed scores as separate events.

Three additional secondary outcomes that will be examined include decline in the cognitive domain factor scores for memory, executive function, and language¹⁴ derived from in-person assessments. Intervention conditions will be compared using the same statistical methods described above for the primary outcome. Results from the analysis of the four secondary outcomes will be included in the primary outcome manuscript.

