## Secondary Outcomes

An important secondary outcome is time until a composite of (1) adjudicated dementia determined from in-person or phone-based evaluations, (2) adjudicated MCI determined from in-person evaluations (3) a 3-point drop in the 30-item MMSE administered in-person, or (4) a 3-point drop in a factor score derived from the 10-item MMSE orientation subscale and 11-item Blessed scale administered over the phone and rescaled to be equivalent to the 30-item MMSE. Intervention conditions will be compared for the time until the composite outcome utilizing a discrete-time, cause-specific proportional-hazards model with a complimentary log-log link. The same baseline covariates specified for the mixed effects model will be integrated into the proportional-hazards model. Time on study will be the time scale. As a sensitivity analysis, we will examine variations of the composite outcome that include (1) adjudicated MCI from phone-

based evaluations and (2) unadjudicated MCI diagnoses identified algorithmically. In exploratory analyses, we will analyze time until (1) adjudicated dementia or MCI diagnosis and (2) decline in MMSE and Blessed scores as separate events.

Three additional secondary outcomes that will be examined include decline in the cognitive domain factor scores for memory, executive function, and language derived from in-person assessments. Intervention conditions will be compared using the same statistical methods described above for the primary outcome. Results from the analysis of the four secondary outcomes will be included in the primary outcome manuscript.

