ACHIEVE is a randomized, open-label trial comparing a hearing intervention versus a successful aging control intervention. The original plan for enrollment was to recruit 850 participants with approximately 425 in each condition. The final enrollment was expanded to 977 participants following a sample size assumption analysis (see section 5.2) conducted in June 2019. Enrollment began in November 2017. Each participant will be followed for 36 months; the COVID-19 pandemic made in-person visits impossible from mid-2020 to mid-2021 delaying the closeout 36 month visit for many participants.

Participants in the hearing intervention condition are fitted with a hearing aid, instructed to be worn on a daily basis for study duration, and attend four 1-hour intervention sessions spaced over the 2-3 months post-randomization. Re-instruction in use of devices and hearing rehabilitative strategies will be provided every 6 months.

The successful aging control intervention consists of four 1-hour intervention sessions spaced over the 2-3 months post-randomization focusing on participant-selected topics from the 10 KeysTM to Healthy Aging program and upper body stretching. Additional sessions will be provided every 6 months.

When spouses or cohabitating partners are both eligible and randomized together, they will be randomized as a unit with, arbitrarily, the first spouse/partner of the pair to be selected according to the random assignment procedure and the second spouse/partner of the pair receiving the same assignment. Spouse/partner pairs will be randomized in spouse/partner-pair specific permuted order blocks of varying sizes within strata defined by participant status (at least one spouse/partner pair in ARIC or both non-ARIC participants) and by field site.

Pre-screening will determine if an individual meets the inclusion criteria. The screening visit is used to consent participants and to determine if an individual meets audiometric, vision, and cognitive inclusion criteria. During the baseline visit assessments measures of primary and secondary outcomes will be collected.

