7.2 Primary Outcome

The primary outcome is cognitive decline, as measured by the change in a global cognitive function factor score. The factor score is derived from a confirmatory factor analysis model that identifies common covariation among all cognitive tests administered in-person. Factor scores are generated for each participant at each in-person assessment using a measure harmonization and item banking approach^{16, 17}. Factor loadings and latent means for each neurocognitive test are estimated using data from the ACHIEVE baseline. The mean of the global cognitive function factor score at the baseline is set to 0 and the SD is set to 1. Fixed parameter estimates from the baseline model are then integrated into models that estimate the factor mean and SD at each subsequent assessment. This process ensures that changes over time represent changes in the underlying factor rather than changes in the scaling or meaning of the constructs. The assumption of longitudinal measurement invariance is supported by prior studies that utilized similar neurocognitive tests^{18, 19}. A final fixed parameter model analyzes available data collected in-person and

computes a global cognitive function factor score for each participant at every assessment in which one or more neurocognitive tests were completed. A comparable process is used to generate factor scores for the cognitive domains of memory, executive functioning, and language.

7.3 **Primary Analysis**

We will examine cognitive decline within each condition using mixed effects models that account for the correlation among repeated measures as well as the correlation between spouses or cohabitating partners. If a linear trend appears reasonable, we will fit a model with a linear slope. If a nonlinear trend is observed, the model will be adapted to include time splines²⁰. Continuous time in years from the baseline will be the time scale. An interaction term between treatment assignment and time will be used to test if rates of cognitive change differ by treatment assignment. Model fit will be assessed with residual plots and other statistics (Akaike Information Criterion, Bayesian Information Criterion, etc.). The primary analysis may include adjustments for the baseline hearing loss, ARIC vs de novo status, center, age, sex, education, and APOE ϵ 4 alleles.

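### No allowance for spouse/partner pairs is specified for the composite time-to-event model, although pairs share one assignment and the primary model accounts for them

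*SAP*

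**What the plan says.** **Randomisation.** When both members of a couple are eligible and enter together, SAP 4 (Study Design) states that "they will be randomized as a unit". The second member takes the first member's arm. Protocol 8 says the same, with separate blocks and strata for pairs.

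**Primary outcome.** SAP 7.3 and Protocol 12.2 use mixed effects models that "account for the correlation among repeated measures as well as the correlation between spouses or cohabitating partners".

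**Domain scores.** For memory, executive function and language, SAP 7.5 says: "Intervention conditions will be compared using the same statistical methods described above for the primary outcome". The pair correlation is therefore covered there too.

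**Composite outcome.** SAP 7.5 names a "discrete-time, cause-specific proportional-hazards model with a complimentary log-log link", and Protocol 12.2 repeats the wording. What passes from the mixed model is stated as follows: "The same baseline covariates specified for the mixed effects model will be integrated into the proportional-hazards model". Time on study is the time scale. No pair random effect, shared frailty, generalised estimating equations or clustered variance is named for this model. None appears in the SAP's sections on power, general considerations, multiplicity or software either.

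**The concern.** For couples the randomised unit is the pair, and both members are always in the same arm. Any positive correlation between their outcomes therefore adds to the variance of the treatment contrast. A complementary log-log model fitted to person-period records gives independence-based standard errors unless clustering is requested. A programmer who followed SAP 7.5 literally would carry over the covariates but not the correlation structure.

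The SAP calls this outcome important, will report it in the primary manuscript, and includes it among the five outcomes in the Hochberg comparison (SAP 7.7 and the version 5.2 change entry). It is the only one of the five without a stated provision for pairs. At stake are a confidence interval for the hazard ratio that is slightly too narrow and a p-value that is slightly too small.

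**Working it through.** **Inputs from the documents.** SAP 5.1: original N = 850; control event rate 0.050 per person-year; 30% reduction, so 0.035 in the hearing arm; 25% of person-time lost; two-sided 0.05; 80% power at a hazard ratio (HR) of 0.54. SAP 4: 36 months of follow-up. Protocol summary: 1:1 allocation.

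**Step 1: the plan's own figure.**
- Expected events = 850 × 3 × 0.75 × (0.050 + 0.035)/2 = 81.3.
- Detectable HR (Schoenfeld) = exp(−(1.960 + 0.842) × 2/√81.3) = 0.537, which agrees with 0.54.
- Power at HR 0.54 is 79.3%.

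The stated figure is reproduced with independent participants, so it contains no design effect for pairs.

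**Step 2: the effect of pairs.** A cluster of two has design effect 1 + ρ and a single participant has 1. With a share f of participants in pairs, the overall design effect is DE = 1 + fρ, where ρ is the within-pair correlation left after covariate adjustment. Then:
- correct SE / naive SE = √DE
- true level of a nominal 0.05 test = 2 × [1 − Φ(1.960/√DE)]
- effective events = 81.3/DE

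Neither f nor ρ is in the documents, so both are assumed. The first three rows span the working range; the last goes beyond it.

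| f | ρ | DE | SE ratio | True level | Detectable HR, N = 850 | Power at HR 0.54 |
|---|---|---|---|---|---|---|
| 5% | 0.05 | 1.0025 | 1.0012 | 0.0503 | 0.537 | 79.2% |
| 10% | 0.10 | 1.0100 | 1.0050 | 0.0511 | 0.535 | 78.9% |
| 20% | 0.30 | 1.0600 | 1.0296 | 0.0570 | 0.527 | 77.0% |
| 30% | 0.30 | 1.0900 | 1.0440 | 0.0605 | 0.523 | 75.8% |

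The SE ratio says how much larger the correct SE is. Put the other way, at the top of the working range the naive SE is too small by 1 − 1/1.0296 = 2.9%.

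**Step 3: simulation check.** A complementary log-log model was fitted to data with same-arm pairs, a shared normal frailty and no treatment effect, with 600 runs per setting.

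| Share in pairs | Frailty SD | Mean naive SE | Mean clustered SE | Ratio | Naive type I error |
|---|---|---|---|---|---|
| 10% | 1.0 | 0.1888 | 0.1901 | 1.007 | 0.050 |
| 20% | 1.0 | 0.1882 | 0.1906 | 1.013 | 0.052 |
| 30% | 1.5 | 0.2051 | 0.2126 | 1.037 | 0.048 |

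The Monte Carlo error of a 5% rejection rate is √(0.05 × 0.95/600) = 0.9 percentage points. The naive rates cannot be told apart from nominal. The SE ratios are of the size that Step 2 gives.

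**The case against.** **Silence is not a decision.** A reader might infer that the sponsor chose to treat spouses as independent. The documents do not support that. They name a model, a link, covariates and a time scale, and no variance estimator. The sponsor may well intend to cluster. This stands, and the point is therefore one of specification. It does not remove the gap, because the text states the pair correlation for one model and leaves it out for the other.

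**The same-methods sentence.** It could be read as covering the composite, but it sits in the following paragraph and refers to the three domain scores.

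**Residual correlation may be low.** Couples tend to share education and testing site. Education and center are among the covariates listed in SAP 7.3, although the wording there is that the analysis may include them. Only correlation left after adjustment matters. No document quantifies it or establishes that it is positive. This stands, and it makes the upper end of the assumed range generous.

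**The effect is negligible.** A reader might infer that type I error is materially inflated or that a Hochberg decision would change. Neither has been shown. In the middle case the SE rises by 0.5% and power at HR 0.54 falls from 79.3% to 78.9%. This stands as to size. The direction, if residual correlation is positive, is still anti-conservative.

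**Conclusion.** The point holds as a minor gap in specification. The composite is the one outcome in the Hochberg set whose stated model makes no provision for pairs, and a literal fit would give an independence-based standard error. The effect is an SE correction of about 0.1% to 3.0% and a true level of at most about 0.057. That rests on the assumed 5-20% of participants in pairs and a residual correlation of 0.05-0.30. If residual correlation is nil, there is no effect. The case for acting is consistency with the plan's own handling of the other four outcomes, at almost no cost; there is no evidence that the result would otherwise be wrong.

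**What to change.** Add to SAP 7.5 and Protocol 12.2 that the composite model, and its sensitivity and exploratory versions, use a robust (sandwich) variance clustered on the spouse/partner pair, with single participants as clusters of one. Report the number of pairs by arm so that readers can judge the effect.

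Do not list a pair-level random intercept as an equivalent option. The sandwich variance leaves the hazard ratio estimate unchanged, whereas a random intercept makes it conditional on the pair and so changes the estimand. Its variance would also be poorly identified, with about 81 expected events at N = 850 and pairs a minority under every share assumed here.

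Cost: one sentence in each document and one program option. No new data are needed, since the primary mixed model already requires the pair identifier.

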		Visit 0 (Day -31 to Day 0)	Visit 1 Day 0	Visit 2 (W1-3)	Visit 3 (W3-5)	Visit 4 (W6-8)	Visit 5 (W8-10)	Visit 6 (6mo)	Visit 7 (12mo)	Visit 8 (18mo)	Visit 9 (24mo)	Visit 10 (30mo)	Visit 11 (36mo)
				A	B	C	D		Yr1		Yr2		Yr3
Adverse event assessment/ Unanticipated problems		X	X	X	X	X	X	X	X	X	X	X	X
CES-D Scale			X 					X	X		X		X
Hearing Handicap Inventory for the Elderly - Screening Version			X 					X	X		X		X
RAND 36-Item Health Survey			X					X	X		X		X
Cohen Social Network Index			X					X	X		X		X
UCLA Loneliness Scale			X					X	X		X		X
Accelerometry			X						X		X		X
Falls and mobility questionnaire			X						X		X		X
Hospitalizations			X					X	X	X	X	X	X
Grip Strength			X 						X		X		X
Short Physical Performance Battery			X 						X		X		X
Physical Activity Form			X						X		X		X
Intervention feedback form								X					X
COVID impact questionnaire 										X	X	X	X
SUCCESSFUL AGING INTERVENTION PARTICIPANTS ONLY													
Successful aging intervention visit/booster session				X	X	X	X	X	X	X	X	X	
HEARING INTERVENTION PARTICIPANTS ONLY													
Hearing Intervention Assessment Outcomes													
Real-ear aided response					X	X 	X 	X 		X 		X 	
Speech Intelligibility Index (aided)					X	X 	X 	X 		X 		X 	
Quick Speech in Noise (aided)							X		X		X		X
Hearing Aid Data Log					X	X	X	X	X	X	X	X	X
International Outcome Inventory for comprehensive intervention							X	X	X	X	X	X	X
Client-Oriented Scale of Improvement				X		X	X						
COMMUNICATION PARTNERS FOR PARTICIPANTS RANDOMIZED TO HEARING INTERVENTION													
Informed Consent Form				X 	X 								
Demographics				X 	X 								
RAND 36-Item Health Survey				X 	X 			X 	X 		X 		X 
International Outcome Inventory – Significant Other							X 		X 		X 		X 
1. Procedures only needed for participants not in ARIC-NCS. 2. Measures shared across ACHIEVE and ARIC-NCS V7. 3. Typically obtained at the baseline visit, but could be obtained at a follow-up visit if not obtained at the baseline visit.													

Assessment	Pre-screening	Screening	Baseline	Intervention and Follow-Up Visits									

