For the secondary outcome of incident cognitive impairment, a dataset was constructed of participants in the ARIC cohort who had comparable characteristics to the individuals enrolled in ACHIEVE, did not exhibit signs of cognitive impairment at the baseline, and who were monitored over a period of 5 to 8 years. The observed rate was 50 cases of incident cognitive impairment per 1000 person-years. Assuming a 30% reduction in the hearing intervention condition and a 25% loss of person-time due to attrition, the proposed proportional-hazards model (described in section 7.5) would have 80% power to detect a hazard ratio of 0.54 when using a 2-sided test and p < 0.05.

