7.1 General Considerations

Study data will be monitored on an on-going basis by the ACHIEVE Data Coordinating Center (DCC). The DCC will send data clarification requests to the clinical sites for resolution while the study is on-going. Final cleaning and editing of the study database will be carried out after the final participant completes their last follow-up visit. Unblinding of treatment assignments will not be performed until the study data are cleaned, queries resolved, and database lock achieved. A permanent archive of the database will be maintained by the DCC. Randomization, stratified by ARIC study status, center, and hearing impairment level is completed within CDART, the DCC's data management system. Built-in algorithms first check for missing key items and eligibility criteria, reducing protocol violations associated with enrollment. Although the ACHIEVE hearing aid intervention is, by nature, un-masked, to minimize bias based on review of accumulating data by the project team, the ACHIEVE PI, co-investigators, and key project staff, except for key data coordinating center staff, will remain blinded to accumulating data. This will be done by applying a dummy ID onto the treatment-specific data forms as they are transferred from CDART to SAS for data cleaning and interim reporting.

This statistical analysis plan (SAP) was developed prior to review of the study dataset and under the assumption that all data were collected in adherence to the protocol and in accordance with good clinical research practices. As the data are analyzed, some deviation is anticipated (e.g., missing data; small sample sizes). In instances where these deviations would make the proposed analyses inappropriate, modifications to the analysis plan will be made and noted in the final report.

Consistent with best practices in clinical trials, we will assess the comparability of the randomized conditions with respect to known baseline confounders, such as hearing loss (pure tone average in the better hearing ear <40 db vs 40+ db), recruitment source (ARIC vs de novo), center, age, sex, education, and the presence of APOE ε 4 alleles⁶. If, despite randomization, there is an imbalance between the treatment conditions we will adjust for relevant confounders as well as explore the use of a precise, locally efficient, augmented, simple estimator⁷ which may offer greater precision.

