7.7 Adjustment for Multiple Comparisons

Statistical significance for the primary outcome will be defined as p < 0.05. Secondary outcomes will be evaluated for statistical significance with a Hochberg modification to the Bonferroni adjustment, in which the p-values of the five outcomes will be ordered. The largest p-value will be compared relative to p < 0.05, and if met, all parameters will be considered significant. If not, then the second largest p-value will be assessed relative to p < 0.05/2 = 0.025, and if met then it and all other parameters will be considered significant, and so on for the 3rd p-value compared at 0.05/3=0.017, the fourth compared to 0.05/4 = 0.012, and the fifth compared to 0.05/5 = 0.01.

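### The hazard model for time to cognitive impairment borrows a covariate list without baseline cognition; pre-specifying it is a modest improvement that costs only wording

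*SAP*

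**What the plan says.** SAP 7.5, repeated in Protocol 12.2 (Secondary Outcomes), compares the arms on time to a four-part composite: adjudicated dementia, adjudicated MCI, a 3-point fall on the in-person MMSE, or a 3-point fall on a phone score rescaled to the MMSE. The model is a discrete-time, cause-specific proportional-hazards model with a complementary log-log link. On covariates it says: "The same baseline covariates specified for the mixed effects model will be integrated into the proportional-hazards model".

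The list it points to is in SAP 7.3 and Protocol 12.2 (Primary Analysis): "The primary analysis may include adjustments for the baseline hearing loss, ARIC vs de novo status, center, age, sex, education, and APOE" ε4 alleles. No baseline cognitive measure is on it, and even the listed variables are introduced as optional.

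Three other places bear on the point:

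- SAP 7.1 checks arm comparability on "known baseline confounders, such as hearing loss" and the other variables of the same list. If, after randomisation, "there is an imbalance between the treatment conditions we will adjust for relevant confounders". Cognition is not named and no threshold for imbalance is given.
- SAP 7.7 puts the composite in a multiplicity-controlled family: "Secondary outcomes will be evaluated for statistical significance with a Hochberg modification to the Bonferroni adjustment".
- Protocol 8 stratifies randomisation by hearing-loss severity, ARIC status and field site (pairs by ARIC status and site), not by cognition.

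**The concern.** The list suits the model it was written for. Under SAP 7.2 a factor score is computed at every in-person assessment, baseline included, so each participant's starting level is part of the repeated outcome in the mixed model. A discrete-time hazard model has rows only for follow-up intervals. Copying the list across therefore removes baseline cognition from the analysis.

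Baseline cognition is a plausible prognostic variable here. MCI requires a domain Z score below -1.5, and dementia can be assigned on a low MMSE (Protocol 7.3), so participants start at different distances from those thresholds. The remaining components are falls measured from the baseline score itself.

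Two things are at stake: some power for an outcome inside the Hochberg family, and protection of its hazard ratio against a chance difference between arms in baseline cognition.

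**Working it through.** **1. The plan's own figure.** SAP 5.1 says the model "would have 80% power to detect a hazard ratio of 0.54 when using a 2-sided test and p < 0.05". Its inputs are N=850, 50 cases per 1000 person-years, a 30% reduction and 25% of person-time lost. SAP section 4 gives 36 months of follow-up.

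- Events = 850/2 × 3 × 0.75 × 0.05 × (1 + 0.70) = 81.3.
- Schoenfeld: √81.3/2 × |ln 0.54| − 1.96 = 4.51 × 0.616 − 1.96 = 0.82, so power = 79.3%.
- Detectable hazard ratio at 80% power = exp(−2 × 2.80/√81.3) = 0.537.

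The figure reproduces with an unadjusted formula. Leaving baseline cognition out therefore does not put power below the figure planned at N=850. Any loss is relative to an adjusted analysis.

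**2. Power with and without the covariate.** A three-visit complementary log-log model was simulated at N=977, with 0.05 events per year in controls, a true hazard ratio of 0.60 and about 73% of person-time retained (79 to 83 events). One standardised covariate stands for the part of baseline cognition not already carried by age, education and the other listed variables. Its hazard ratio per SD is an assumption, because the documents give none.

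| Assumed HR per SD | Power without | Power with | Gain (points) | Mean HR without | Mean HR with |
|---|---|---|---|---|---|
| 1.25 | 62.9% | 64.2% | 1.3 | 0.592 | 0.591 |
| 1.5 | 60.4% | 61.1% | 0.7 | 0.603 | 0.600 |
| 2.0 | 60.0% | 63.2% | 3.2 | 0.606 | 0.596 |
| 2.5 | 56.6% | 60.9% | 4.3 | 0.615 | 0.598 |
| 3.0 | 52.6% | 60.2% | 7.6 | 0.625 | 0.598 |

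The first row uses 1,500 runs and the others 3,500. The Monte Carlo error of one power figure is about √(0.6 × 0.4/3500) = 0.8 points, or 1.2 in the first row. Both models were fitted to the same simulated trials. At N=850 and a true hazard ratio of 0.54, the gain was 0 to 5 points for hazard ratios per SD up to 2.5.

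The gain is the relevant column. The power levels depend on the attrition assumed and are no test of the 80% in SAP 5.2.

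**3. Opposing signs.** A low starting level should raise the risk of MCI and dementia, whereas a high observed MMSE leaves more room for a 3-point fall through regression to the mean. With assumed log hazard ratios of 0.3 to 1.1 in opposite directions for the two scores, and a correlation of 0.5 between them, adding both scores gained only about 0 to 2 points. Each score still carried its own effect.

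**4. Type I error.** At a true hazard ratio of 1.0 (1,500 runs per setting, hazard ratio per SD 1.0 to 2.5), rejection was 4.5% to 5.4% without the covariate and 4.5% to 5.5% with it.

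**5. Chance imbalance.** With equal arms, and ignoring pairs, the standard error of the arm difference in a standardised baseline score is 2/√977 = 0.064 SD. Then 1.96 × 0.064 = 0.125 SD. To first order the unadjusted hazard ratio is multiplied by (HR per SD)^0.125:

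- 1.5 gives 1.05; a hazard ratio of 0.60 would read 0.63.
- 2.0 gives 1.09; it would read 0.65.
- 2.5 gives 1.12; it would read 0.67.

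An imbalance in the other direction divides by the same factor.

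**The case against.** The case for leaving the plan alone is substantial.

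- **Prognostic strength is unknown.** A reader might infer that baseline cognition is the strongest measured predictor and largely decides who has an event. No passage says so. MCI also requires decline, entry has an MMSE floor of 23 or 25 (Protocol 4.1), and the fall components can reverse the direction. In an illustration with assumed inputs (MMSE error SD 0.8 to 1.3; level-based events at 0.02 to 0.04 per year with hazard ratio 0.5 per SD), the net hazard ratio per SD of baseline MMSE ran from 0.77 to 1.22. This objection stands and limits the size.
- **The unadjusted hazard ratio is not biased.** Its drift toward 1 is non-collapsibility, and it remains a valid estimand. This stands.
- **Imbalance is not unguarded.** A reader might infer that it passes unchecked into the result. Randomisation holds the overall error rate, SAP 7.1 promises adjustment if imbalance is seen, and listed covariates may carry part of the information. This stands in part. The fallback does not name cognition, has no threshold, and would be decided with arm-level data in view, which is weak for an outcome in the Hochberg family.
- **Missing APOE genotypes.** A reader might also infer that ungenotyped participants fall out of this model, since the sample "could be obtained at a follow-up visit if not obtained at the baseline visit". The documents do not establish that. ARIC participants were already genotyped (Protocol 7.4.6), no count of missing genotypes is given, and SAP 7.3 places the listed covariates in the imputation model, though it does not say whether the hazard model uses those datasets.

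**Conclusion.** The omission is real: the borrowed list has no baseline cognitive score, the hazard model has no other route for one, and the only fallback is conditional. The consequence is modest. Expect about 0 to 4 points of power for a prognostic hazard ratio per SD up to 2.5, and about 8 points at 3.0. A 1.96-standard-error imbalance shifts the unadjusted hazard ratio by about 5% to 12% for prognostic hazard ratios of 1.5 to 2.5. These ranges rest on assumed prognostic strengths and on a covariate effect beyond the listed variables.

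The stronger readings, that the test is invalid or that the plan misses its stated power because of this omission, are not supported. The argument rests mainly on pre-specification and protection from imbalance; power is secondary.

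**What to change.** In SAP 7.5 and Protocol 12.2 (Secondary Outcomes), state that the proportional-hazards model will include the baseline global cognitive function factor score and baseline MMSE, both continuous, in addition to the mixed-model covariates. This replaces reliance on the conditional adjustment in SAP 7.1 for these two variables. Report the model without them as a sensitivity analysis. Do not add a not-genotyped category for APOE: late sampling is possible only in people who return, so membership would depend partly on retention after randomisation.

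The cost is wording in two places, settled before unblinding. Both measures are already scheduled at baseline (Protocol 7.7, Table 3). The one small downside is that the hazard ratio becomes conditional on baseline cognition, and the sensitivity analysis covers that.
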